8.5. Regional LV function

Improvement in regional function will be defined as an improvement in mean wall motion score index ≥ 0.5 across a coronary vascular territory, and by improvement in wall motion score index ≥ the median change. Vascular territories will be defined according to the AHA 17 segment model⁹. The frequency of functional recovery will be compared between territories which were and were not revascularised based upon scar burden, median wall thickness and the proportion of viable segments or ischaemic segments within the subtended territory. A Cox regression analysis will be used to determine the factors best predictive of functional recovery. The analysis will be conducted in three cohorts; the first within the whole trial population, the second solely within those assigned to receive PCI, and the third in all those vascular territories which met trial-defined criteria for viability (median scar burden ≤ 25%).

8.6. Cardiac morphology and clinical outcomes

Median values for left and right ventricular volumes, stroke volume and left ventricular mass will be determined from the dataset. Kaplan-Meier curves for the primary outcome will be constructed separated by median values for each feature of cardiac morphology. A Cox regression analysis will be performed to determine whether these factors have an independent impact on clinical outcome, adjusted for treatment assignment, scar burden and other clinical factors, incorporating tests for interaction.

8.7. Inducible ischaemia

The burden of inducible ischaemia predicts future adverse cardiac events in patients with ischaemic heart disease¹⁰. CMR allows assessment of ischaemic burden through stress perfusion imaging, typically with adenosine vasodilatation, a diagnostic strategy which is equivalent to both nuclear

perfusion imaging and invasive assessment in patients with stable coronary artery disease and normal left ventricular function^{11,12}. Several randomised trials have assessed whether the presence of inducible ischaemia, or the burden of inducible ischaemia, can identify patients with stable coronary artery disease who may benefit from revascularisation, with no significant interaction found in studies to date^{13,14}; these trials excluded patients with severely impaired left ventricular function and data the question remains unanswered in this population. Perfusion defects will be defined as delayed subendocardial or transmural contrast inflow for at least five dynamic images after contrast agent arrival in the LV cavity. The perfusion defect needs to extend beyond areas of scar identified on LGE imaging and not be matched on resting images, where available. For quantitative analysis, ischaemia will be defined by absolute myocardial blood flow at stress less than 1.9 ml/min/gram of tissue (or normative values for the specific sequence used)or myocardial perfusion reserve less than 2, where rest images are available.

The extent of inducible ischaemia will be determined on a per-patient basis. Ischaemic burden will be compared with myocardial jeopardy by converting both values to percentages of total LV volume (assuming a jeopardy score of 12 = 100% ischaemic burden. Kaplan-Meier plots for the primary outcome will be constructed based upon the presence/absence of significant inducible ischaemia (at least 1 segment of transmural ischaemia or 2 subendocardial segments in the same coronary territory) and based on the presence of ischaemia in >1 coronary vascular territory and separated by treatment assignment. A Cox regression model will be used to determine the effect of ischaemic burden on the primary outcome, key secondary outcomes and on global functional recovery, adjusted for treatment assignment and other key prognostic variables. A repeated measures ANOVA will compare the likelihood of functional recovery between segments with and without ischaemia, accounting for repeated measures in the same patient. A Cox regression model will be used to test for interaction between the presence of inducible ischaemia and segmental functional recovery, adjusted for segmental scar transmurality, wall thickness and revascularisation status. Further analyses will be performed where segmental ischaemia is defined as either a visible perfusion defect or a dysfunctional and viable segment¹⁵.

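### The exploratory ischaemia analysis (Viability SAP 8.7) raises who benefits from revascularisation, but its models estimate only the prognostic association of ischaemia, and its one stated interaction pairs a predictor with its outcome

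*Protocol*

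**What the plan says.** Section 8.7 (Inducible ischaemia) is in Appendix 1 of the Viability Study SAP. Its background first notes that ischaemic burden predicts later cardiac events. It then turns to whether ischaemia "can identify patients with stable coronary artery disease who may benefit from revascularisation, with no significant interaction found in studies to date", and adds that "these trials excluded patients with severely impaired left ventricular function and data the question remains unanswered in this population".

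The analyses specified after that are:

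- Kaplan-Meier plots of the primary outcome by ischaemia status, separated by treatment assignment. No test is attached.
- A patient-level model: "A Cox regression model will be used to determine the effect of ischaemic burden on the primary outcome", and also on "key secondary outcomes and on global functional recovery, adjusted for treatment assignment and other key prognostic variables".
- A repeated measures ANOVA comparing segmental recovery between segments with and without ischaemia.
- A segment-level model: "A Cox regression model will be used to test for interaction between the presence of inducible ischaemia and segmental functional recovery". Here the plan lists revascularisation only among the covariates, the model being "adjusted for segmental scar transmurality, wall thickness and revascularisation status".

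Section 8.1.3 lists inducible ischaemia among the exploratory analyses in subsets, subject to the source data available.

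**The concern.** Whether ischaemia identifies patients who benefit is a question of effect modification: does the PCI hazard ratio change with ischaemia? The section's own background uses that language when it describes earlier trials by their interaction results. A model with ischaemia and treatment as separate main effects answers a different question, namely whether ischaemia predicts events averaged over the two arms.

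The segment-level sentence has a separate defect. An interaction is between two predictors. Ischaemia and segmental recovery are a predictor and its outcome, so the sentence describes an ordinary association. Revascularisation status, the natural partner for ischaemia, is listed only as an adjustment variable.

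At stake is what this appendix can report. Followed literally, it would give an estimate of prognosis and a set of curves, with no estimate or interval for the quantity that its background calls unanswered. Any interaction fitted later would be unplanned, in a small subset where there are several ways to define ischaemia.

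**Working it through.** **1. The model terms side by side.**

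| Viability SAP section | Factor | Partner in the stated interaction |
|---|---|---|
| 7.1 (event-free survival) | Viability | Randomised treatment |
| 8.4 (segmental function) | Scar transmurality or burden | Provision of revascularisation |
| 8.6 (morphology) | Volumes, stroke volume, mass | Tests for interaction included, partner not named |
| 8.8 (arrhythmia) | Viability or scar burden | Treatment assignment |
| 8.7, patient level | Ischaemic burden | None; treatment is a covariate |
| 8.7, segment level | Presence of ischaemia | Segmental recovery, which is the outcome |

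Section 8.2 imports the methods used earlier in the plan. Section 8.7 has no such clause, so the missing term cannot be filled by reference.

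**2. What the main-effects model returns.** With log hazard = b1 × treatment + b2 × ischaemia, the treatment hazard ratio is exp(b1) whatever the ischaemia level. Adding b3 × treatment × ischaemia gives exp(b3), the ratio of the treatment hazard ratio with ischaemia to that without.

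This was checked by a large-sample simulation: 40,000 patients, 1:1 allocation, 36% two-year event risk on OMT without ischaemia (the 36% is the OMT figure in protocol section 8.1), assumed 50% ischaemia prevalence, and assumed censoring spread uniformly over 2 to 8.5 years.

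- Truth A (assumed): PCI hazard ratio 1.0 without ischaemia and 0.7 with it; ischaemia hazard ratio 1.2 on OMT.
- Truth B (assumed): PCI hazard ratio 0.84 for everyone; ischaemia has no effect.

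| Estimate | Truth A | Truth B |
|---|---|---|
| Treatment HR, main effects only | 0.84 | 0.85 |
| Ischaemia HR, main effects only | 1.01 | 1.02 |
| Ratio of HRs, product term added | 0.72 | 1.00 |

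The simulated values agree with a simple approximation. Under A the main-effects treatment estimate is about √(1.0 × 0.7) = 0.84, and the ischaemia estimate is about √(1.2 × 1.2 × 0.7) = 1.00. The model as specified barely separates the two truths; the product term does.

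**3. Precision of the added term.** Section 8.7 states no sample size or power, so it has no figure to reproduce. The only figure borrowed is the main trial's 300 events in 700 patients. That plan reproduces: Φ(√(300/4) × |ln 0.7| − 1.96) = Φ(3.09 − 1.96) = 87%, against the stated figure of over 85%.

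With events split equally over the four treatment-by-ischaemia cells, the variance of the log ratio is 4 × 1/(E/4) = 16/E. The Viability SAP (section 4.1) gives 491 patients with CMR viability assessment, which is the ceiling for the perfusion subset. Pro rata, E = 491 × 300/700 = 210, so SE = √(16/210) = 0.276. For a ratio of 0.7, power = Φ(0.357/0.276 − 1.96) = Φ(−0.67) = 25%. The 95% interval is the estimate divided and multiplied by exp(1.96 × 0.276) = 1.72, so an estimate of 0.7 would run from 0.41 to 1.20.

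| Patients with perfusion data | Events | Power, ratio 0.7 | 0.6 | 0.5 |
|---|---|---|---|---|
| 491 (ceiling) | 210 | 25% | 46% | 71% |
| 250 (assumed) | 107 | 15% | 26% | 43% |
| 150 (assumed) | 64 | 11% | 17% | 28% |

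**The case against.** The strongest reply is about status. The formal objectives of the Viability SAP concern viability and do not mention ischaemia. The benefit question is in the background of 8.7 beside a prognostic question, and the specified Cox model does address the prognostic one. The analysis is exploratory, in an appendix of later analyses. The study's primary effect-modification question, about viability, has explicit interaction models in 7.1 and 7.2. All of this stands, and it limits the importance of the point. It does not supply the missing term.

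The segment-level sentence is probably a drafting slip, since 8.4 sets out the parallel scar model correctly. That is likely, but the sentence as signed cannot be carried out as an interaction test. Section 8.5 also compares recovery between revascularised and non-revascularised territories using, among other things, the proportion of ischaemic segments. That brings ischaemia and revascularisation together at territory level, but it names no interaction test.

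Low power is a fair caution about what the added term can show. It supports reporting an estimate with an interval more than a p-value, and it is no reason to leave the estimate out.

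A reader might infer that the section cannot speak to benefit at all. That goes too far, because the plots by arm allow a descriptive comparison. A reader might also expect the plots to be used to claim effect modification from a difference in significance. The documents do not support that: no test is attached to the plots, and nothing says that such a claim will be made. Nor should 8.6 be cited as a section that names a treatment interaction, because it does not name the interacting factor.

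**Conclusion.** The point holds in a limited form. As specified, the models in 8.7 estimate whether ischaemia predicts events or recovery. None estimates whether it changes the effect of PCI, although the section gives that as part of its rationale and calls it unanswered in this population. The segment-level interaction is wrong as written.

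The finding about model terms rests on the text alone. The simulated hazard ratios rest on assumed effects and show only that a main-effects model does not separate the two situations. The power figures rest on an assumed 50% ischaemia prevalence, pro-rata events and, below 491, assumed subset sizes; the documents give neither the prevalence nor the number with perfusion data. The main trial analysis and the primary viability analysis are unaffected.

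**What to change.** In 8.7:

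1. Add ischaemic burden × randomised treatment to the patient-level Cox models for the primary and key secondary outcomes, as 7.1 does for viability, and the same term to the model for global recovery. Report the ratio of hazard ratios with a 95% confidence interval, and give the treatment hazard ratio by ischaemia group beside the Kaplan-Meier plots.
2. Restate the segment-level test as ischaemia × revascularisation on segmental recovery. Use assignment to PCI as the first definition of revascularisation and documented successful revascularisation as the second, following 8.4.
3. Label the results exploratory, state the number of patients and events with perfusion data, and interpret the interval. If the change is made after ischaemia results by arm have been seen, identify it as unplanned, as section 6.1 of the main SAP requires for such analyses.

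The cost is one product term per model and a few sentences of SAP text, with no new data. The drawback is a wide interval, which will probably not settle the question.

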8.8. Ventricular arrhythmias

Infarcted myocardial tissue provides an abnormal electrophysiological substrate, which can allow generation of re-entry circuits and ventricular tachycardia and/or fibrillation. Sudden death from these scar-related ventricular arrhythmias is one of the leading causes of death in the ischaemic

cardiomyopathy cohort. This large, curated cohort provides an invaluable opportunity to assess how scar characteristics predict and relate to arrhythmic risk.

Data relating to indication and timing of ICD and CRT insertion, appropriate and inappropriate therapies and sustained ventricular arrythmias were collected via a dedicated arrhythmia case report form (CRF) during the trial.

The primary outcome of this arrhythmia analysis will be a composite of all-cause death or aborted sudden death (defined as an appropriate ICD therapy or a resuscitated cardiac arrest). A Cox proportional hazards model will be used to assess the relationship between the number of viable segments/volume of myocardial scar and the primary outcome. The analysis will be adjusted for baseline factors listed in section 7.1. The interaction between viability/scar burden and treatment assignment on the primary outcome will then be assessed using a Cox proportional hazards model where randomly assigned treatment, their interaction and the baseline risk factors listed above are included in the model.

Secondary outcomes will include cardiovascular death, appropriate ICD therapies, total number of appropriate therapies and sustained ventricular arrhythmia(s) (any ventricular fibrillation OR ventricular tachycardia >100bpm that lasts for more than 30 seconds OR requires termination in less than 30 seconds due to hemodynamic compromise).

CMR predictors of arrhythmia (scar burden, LV volumes, LV ejection fraction) will be entered into a Cox regression model along with clinical and ECG predictors of risk, to determine which factors best predict the occurrence of sudden death and ventricular arrhythmias.

Exploratory analyses will be performed to relate novel measures such as scar border zone (defined as signal intensity \geq 2SD around an area of scar) and scar entropy to the occurrence of ventricular arrhythmias¹⁶.

Appendix 2: Dobutamine Stress Echocardiography Secondary Analyses

This appendix describes subsequent planned analyses based on DSE data alone.

9.1. Analysis of DSE viability to predict outcomes

An analysis which reproduces the main viability study outlined above, consisting of the DSE assessed viability alone.

9.2. Wall motion score index prediction of LV recovery and mortality

The wall motion score index (WMSI) is a unitless number that is proportional to the severity and extent of wall motion abnormalities on stress echocardiography calculated by dividing the sum of the individual segment scores by the total number of segments scored. A WMSI >2.19 has been shown to be predictive of mortality or poor functional result in patients undergoing surgical revascularisation however this has yet to be tested in patient undergoing percutaneous coronary revascularisation. ROC curves will be constructed to identify a cut-off WMSI predicting poor outcomes in those undergoing percutaneous revascularisation.

9.3. Relationship between the number of viable segments on DSE and improvement in LV function following revascularisation

Using the AHA 16 segment model for analysis of regional wall motion score will allow the relationship between the total number of viable segments and global improvement in LV function to be explored; additionally segmental recovery will also be assessed using paired student's T test.

9.4. Comparison of sustained improvement in wall motion vs biphasic response of segments in predicting LV recovery

A biphasic response to dobutamine ("low vs high dose") has been found to be a more sensitive predictor of myocardial viability as compared with sustained improvement, moreover the biphasic response was found to be a predictor of global improvement in LV function after surgical revascularisation¹⁸. A comparison of sustained improvement vs biphasic response utilising Cox regression analysis will be carried out to identify if a biphasic response is a more sensitive predictor of myocardial recovery following percutaneous coronary revascularisation.

10. References

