Imaging and intervention specialists at each participating centre will adjudicate segmental viability and the feasibility of revascularising the relevant segments, to determine whether an individual patient will be eligible for randomisation.

12. Randomisation

Potential patients will be reviewed by the Principal Investigator before randomisation with all available tests/notes to confirm eligibility.

Once the eligibility of a patient is confirmed by the trial coordinators and written informed consent obtained, randomisation will be carried out via an online web based system. Randomisation of the treatment assignment will be stratified by centre using randomly permuted blocks of varying size, with 1:1 allocation between the PCI and OMT arms.

There is no time limit from randomisation to PCI. However, it is recommended that index PCI be carried out as close as possible to randomisation to minimise the incidence of major adverse cardiovascular events (MACE) prior to the assigned treatment. Clinical events that occur after randomisation but before planned PCI will be attributed to the assigned treatment on an intention-to-treat basis.

13. Percutaneous Coronary Intervention

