4.1. Sample size

In REVIVED-BCIS2 all patients underwent viability imaging prior to randomisation; at least four viable segments which could be revascularised by PCI were required for inclusion. Of the 700 patients enrolled, viability was assessed with CMR in 491 and DSE in 187. Primary outcome data are available for 99.1% of patients. Serial echocardiographic data are available for a subset of these patients.

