8.4. Segmental LV function

Improvement in segmental function will be defined as an improvement in wall motion score ≥1 grade at follow-up. The frequency of functional recovery will be compared between segments based on scar transmurality/scar burden across time points using a repeated measures ANOVA to adjust for repeated measures within the same patient and over three time points of baseline, six months and one year. An unadjusted Cox regression model will be used to test for an interaction between scar transmurality/scar burden and the provision of revascularisation and the likelihood of functional recovery, adjusted for baseline segmental wall motion. Two models will be used for revascularisation; the first where all segments will be considered revascularised in patients who were assigned to PCI, the second where only segments where a territory was documented as having been successfully revascularised in the eCRF, with the attribution of segments based on the standard American Heart

^{*}indexed to body surface area

Association 17-segment model adjusted for dominance of the circumflex or right coronary artery ⁹. Equivalent analyses will also be performed with scar transmurality/scar burden substituted for end diastolic wall thickness/end systolic wall thickness, as well as for different thresholds of LGE for viability (≤50% and ≤ 75%) and where scar burden is treated as a continuous variable. Receiver-operator characteristic curve analysis will be used to examine diagnostic utility, with Youden's index used to calculate the LGE threshold for optimum sensitivity and specificity to predict functional recovery. DeLong's method will be used to compare ROC curves for the prediction of recovery between the FWHM and 5SD methods of defining regions of myocardial scar.

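### Viability SAP 9.2 calls WMSI >2.19 untested after PCI, but plans only a search for a new cut-off, with no test of 2.19, AUC interval or optimism correction

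*Protocol*

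**What the plan says.** Viability Study SAP section 9.2 sits in an appendix limited to one modality: "This appendix describes subsequent planned analyses based on DSE data alone". It opens with an external threshold: "A WMSI >2.19 has been shown to be predictive of mortality or poor functional result in patients undergoing surgical revascularisation". It then states the gap: "this has yet to be tested in patient undergoing percutaneous coronary revascularisation". The one analysis that follows is: "ROC curves will be constructed to identify a cut-off WMSI predicting poor outcomes in those undergoing percutaneous revascularisation".

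The section does not say what counts as a poor outcome, over what period, or by what rule the cut-off is chosen. It mentions no AUC, interval, test or internal validation. No other section covers WMSI as a predictor.

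Section 8.4, in the CMR appendix, also derives a threshold from the trial data, "with Youden's index used to calculate the LGE threshold for optimum sensitivity and specificity to predict functional recovery". It does so alongside other analyses that 9.2 lacks.

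**The concern.** The stated gap and the stated analysis do not meet. The section names a threshold that awaits testing in PCI patients, and then plans to look for a different one.

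The search has two weaknesses. A best point on a ROC curve exists in every dataset, including one where WMSI carries no information. And if sensitivity and specificity at that point are read from the patients who chose it, they are too favourable on average.

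At stake is a PCI-specific WMSI threshold, derived from fewer than 100 patients and reported with overstated accuracy, while the one threshold fixed in advance goes without a committed test.

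**Working it through.** **The plan's own figure.** The only number in 9.2 is 2.19. It comes from a cited source and cannot be recomputed from the documents. The section gives no sample size, AUC target or error rate to reproduce.

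**Inputs from the documents**
- DSE patients: "viability was assessed with CMR in 491 and DSE in 187" (Viability SAP 4.1).
- Allocation: "with 1:1 allocation between the PCI and OMT arms" (protocol section 12, Randomisation). So about 187 / 2 = 93.5 DSE patients are in the PCI arm, before any loss to uninterpretable scans.
- WMSI scale: the sum of segment scores divided by the number of segments (9.2), with integer scores 1 to 5 (5.1) and 16 segments (4.2 and 9.3). WMSI therefore moves in steps of 1/16 = 0.0625 when all segments are scored. Since 35/16 = 2.1875 and 36/16 = 2.25, >2.19 means a segment sum of at least 36.
- Share with a poor outcome: 27% is the illustrative two-year PCI rate in protocol 8.1. About 50% follows if the outcome is non-recovery, because recovery is defined as above the median LVEF change (Viability SAP 6.2).

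**Assumptions**
- WMSI is roughly normal, mean 2.2, SD 0.35, rounded to the 1/16 grid.
- The cut-off maximises Youden's J = sensitivity + specificity − 1. This rule is borrowed from 8.4, as 9.2 names none.
- High WMSI is the poor direction.
- A 40% outcome share is added as an intermediate value.

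**Method.** WMSI was simulated independently of outcome, 4,000 datasets per setting. In each:
1. Choose the cut-off with the largest J.
2. Apply that cut-off to a fresh dataset of the same size.
3. Compute the uncorrected chi-square, N(ad − bc)² / (product of the four margins), at the chosen cut-off and at fixed >2.19.

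**Results at n = 94** (27% of 94 is about 25 poor outcomes; 50% is 47)

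| Poor outcome | Apparent J above 0 | Mean apparent J | 90th percentile of J | Mean J on new data | Chosen cut-off, 5th to 95th percentile | p<0.05 at chosen cut-off | p<0.05 at fixed 2.19 |
|---|---|---|---|---|---|---|---|
| 27% | 97.7% | 0.116 | 0.215 | −0.002 | 1.56 to 2.81 | 15.1% | 4.5% |
| 40% | 97.7% | 0.105 | 0.196 | 0.000 | 1.56 to 2.81 | 15.7% | 4.9% |
| 50% | 98.2% | 0.103 | 0.191 | −0.002 | 1.50 to 2.81 | 15.1% | 4.9% |

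**Range.** Over n = 60, 80, 94 and 187 and outcome shares of 20% to 50%, mean apparent J runs from 0.07 to 0.17. The chosen cut-off gives p<0.05 in 14% to 17% of datasets, and fixed 2.19 in 4.5% to 5.6%. With 4,000 runs, simulation error is about ±1.96 × √(0.15 × 0.85 / 4,000) = ±1.1 points near 15%, and ±0.7 points near 5%, so the fixed cut-off is consistent with the nominal 5%.

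**The case against.** **No test at the derived cut-off is planned.** This stands. A reader might infer from the simulation that 9.2 carries an inflated false-positive rate. It does not: the 14% to 17% describes a follow-on comparison that the section does not announce. It also depends on the test, falling to about 8% to 9% at n = 93 with a continuity correction. What follows more directly from the text is the optimism in apparent accuracy.

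**The scale and population limit the size.** This stands. Treating WMSI as continuous pushes the hypothetical rate to about 21% to 23%, but the SAP's definition puts WMSI on a grid. All 187 DSE patients would be the wrong base, because 9.2 concerns only those undergoing PCI.

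**A ROC curve is not blind to lack of discrimination.** This stands in part. A useless WMSI would give a curve near the diagonal, and the accuracy of 2.19 can be read off the same curve. But 9.2 commits to neither reading and states its aim as finding a cut-off.

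**Section 8.4 might be thought to have the same fault.** The documents do not support that. It compares recovery by scar extent, fits an interaction model, repeats analyses at fixed thresholds (≤50% and ≤75%, beside the ≤25% definition in 5.2) and compares curves by DeLong's method. It shares with 9.2 only the missing optimism correction. The figures above do not carry over to its segment-level CMR data.

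**The consequence is small.** This stands. It is one sentence in an appendix of secondary analyses.

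**Conclusion.** The point holds as a cheap improvement to a secondary analysis. Section 9.2 names 2.19 as untested after PCI, commits to no test of it, and plans a data-driven search without an AUC interval or optimism correction.

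Under no association, with about 94 PCI-arm DSE patients, that search would show a mean Youden index of about 0.10 to 0.12 where the truth is 0, at a cut-off anywhere from about 1.5 to 2.8. This rests on the assumed WMSI distribution, outcome share, usable sample and Youden rule. The direction is the same in every setting tried, and the size varies from 0.07 to 0.17.

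Nothing here touches the main trial's primary result or the viability study's primary or key secondary outcome.

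**What to change.** In Viability SAP 9.2:
- Make the main analysis the AUC with 95% CI in patients undergoing PCI, together with the sensitivity and specificity, with CIs, of the pre-stated >2.19 cut-off.
- Define the poor outcome and its time horizon, and name the rule for choosing any new cut-off.
- Label any newly derived cut-off exploratory, and report its sensitivity and specificity after bootstrap optimism correction, repeating the cut-off search in each resample.

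In 8.4, add only the optimism correction for the Youden LGE threshold, resampling patients rather than segments because segments cluster within patients.

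The cost is a few sentences and a bootstrap, with no new data. The downside is a little more analysis work and less favourable reported accuracy.
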